1. Counseling twice weekly on diet and nutrition will improve food choices to more healthy choices of fresh fruits and vegetables and low fat protein sources. To test this hypothesis, patients will undergo a food frequency questionnaire at baseline to document choices prior to intervention. A food frequency questionnaire will be performed at the end of the intervention to determine the effect of counseling on protein source, number of calories, and frequency of fresh fruits and vegetables. Counseling will consist of the diabetes prevention program counseling which is a well-established, well-verified intervention, commonly accepted as an effective means of providing a standardized nutritional education.

2. The combination of exercise and dietary intervention positively affects body composition. With this hypothesis we will test whether muscle strength (Biodex measurements) and muscle mass (DEXA scan) changes after 12 months of an exercise intervention. We hypothesize that the transplant itself will not affect activity levels, strength levels or muscle mass. Baseline measurement will be performed before the intervention, at 6 months post intervention, and the final measurement would be taken at 12 months with muscle mass measured by DEXA and strength measured again by Biodex.

3. Patients receiving strength training will have significantly higher activity levels when compared with no intervention or physical therapy. The rationale for this hypothesis is that patients without strength training will fail to increase muscle mass and strength and this inability will translate to persistently lower activity levels than those patients with strength training. Once again levels will be documented with an accelerometer and PROMIS questionnaires, 6 months and 12months to document the effect of intervention. In addition, if patients in the control group and GH group decide to

have the optional muscle biopsy, it will help evaluate how targeted exercise may change muscle development measuring expression of mature microRNAs using total RNA extraction.

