- Control group: patient will be treated according to the standard of care for post-transplant recipients; control patients will be offered the opportunity to undergo the GH regimen for the 1 year after their final visit as a control patient. If the control patients chose to undergo the GH regimen, the extended follow up will be completed after 1 year from their final GH visit (totaling 4 years from the start of intervention).

Long-term follow-up

After the 12 month intervention period all patients will be followed for 2 additional years. Patients will be contacted by phone to assess current activity level, employment status, graft function and current weight. Patient's medical records will also be reviewed to confirm BMI and graft function. This will be done every 6 months.

A separate waiver of documentation of consent, for long-term follow up, is being requested for patients that have previously enrolled and completed the study (January 3, 2012 to July 28, 2014).

Parameters to analyze in all patients:

The PROMIS v.1.1 - Global Health short form will be administered to all patients at the time of enrollment, 6 months and at the end of the study (12 months). The PROMIS v.1.1 - Global Health short form will assesses health in general (i.e. overall health). The PROMIS Global Health short form is a 10-item instrument representing multiple domains (physical function, fatigue, pain, emotional distress, social health) as well as perceptions of general health that cut across domains. Global items allow respondents to weigh together different aspects of health to arrive at a “bottom-line” indicator of their health. Similar global health items have been found predictive of future health care utilization and mortality.

PROMIS 29 Profile v2.0 will be administered to all patients at the time of enrollment, 6 months and at the end of the study (12 months). The PROMIS 29 Prolife v2.0 is a short form containing four items from seven PROMIS domains (Depression, Anxiety, Physical Function, Pain Interference, Fatigue, Sleep Disturbance, and Ability to Participate in Social Roles and Activities) along with a single item on Pain Intensity.

Multiple studies have been conducted by the PROMIS Network validating these instruments. Studies are shown at: <http://www.nihpromis.org/science/validitystudies.aspx>

Body composition and strength

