BMI will be calculated at the time of enrollment, at 6 months, and at the end of the study (12 months). The most exact method to determine body fat and lean body mass is DEXA, a method that has been validated in patients with renal failure before and after transplantation [6,7]. Waist circumference as well as blood pressure will be measured for general health markers. Muscle strength will be measured using a Bidex machine. Exercise capacity will be measure with a 6 minute walk test and an accelerometer. Fitness level will be measure with a maximal aerobic capacity test (VO₂ max). These 7 tests will be done at baseline, 6, and 12 months.

Waist Circumference:

Waist circumference will be measured at the narrowest part of the torso (above the umbilicus and below xiphoid process) in the standing position using a tape measure. This will be completed at baseline, 6 months and 12 months post-intervention.

Blood Pressure:

Blood pressure will be measured in the supine position (lying on back) in a dimly lit room after resting for fifteen minutes. This will be completed at baseline, 6 months and 12 months post-intervention.

DEXA Scan: We will determine percent body fat via a whole body scan by dual energy x-ray absorptiometry (GE, IDX, Madison, WI), which will be operated and calibrated using the manufacturer's stated guidelines. The duration of the scan will be less than 10 min and the subject will be exposed to a radiation dose of ≤ 0.3 mrem based upon the manufacturer's specifications and calculations from Standford Dosimetry, LLC RADAR Medical Procedure Radiation Dose Calculator. This amount of research protocol radiation exposure is minimal given the estimated effective equivalent dose is below the 100 mrem per year, a limit set by the Nuclear Regulatory Commission for "general public" exposure.

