We will look at the artery in the subject's neck using an ultrasound machine. This machine is similar to what doctors use to look at babies within the womb. We will place a small amount of gel on their neck to help us get a clearer picture. This gel is hypoallergenic and washes off very easily. We will place the probe on their skin, over the artery on the inside of their right neck. This probe will allow us to look at the carotid artery and see how it moves with each heart beat. This test will be performed at baseline, 6 months and 12 months post-intervention.

Cardiac Ultrasound

We will measure the subject's heart function with ultrasonography using ultrasound gel and a probe. It is the same probe used to visualize babies in the womb. We will measure

how quickly the subject's heart contracts and relaxes. This test will be performed at baseline, 6 months and 12 months post-intervention.

Other measurements: Resting heart rate will be measured in the supine position. Resting blood pressure will be measured in the brachial artery using a digital sphygmomanometer in the supine position according to the guidelines of the American Heart Association. Blood pressure will be measured twice, one minute apart, and the average of the two values will be used as resting blood pressure. Body mass index will be calculated as weight (kg) divided by height (m) squared. Employment status will be confirmed. These measures will be completed at baseline, 6 months and 12 months post-intervention.

GH subjects only:

Personality Assessment

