Week 42	1 Warm Up Set: 8 – 12 reps. 1 Heavy Set: 8 – 12 reps. Slower Speed.	Moderate/Heavy	2 minutes
Week 43	3 Sets on each exercise of 6, 8, 12 repetitions. Lower weights each set. Medium speed.	Moderate	3 minutes
Week 44	1 set 90 seconds focused on resistance. Medium speed.	Lighter	2 minutes
Week 45	1 Warm Up Set: 8 – 12 reps. 1 Heavy Set: 8 – 12 reps. Slower Speed.	Moderate/Heavy	2 minutes
Week 46	3 Sets on each exercise of 6, 8, 12 repetitions. Lower weights each set. Medium speed.	Moderate	3 minutes
Week 47	1 set 90 seconds focused on resistance. Medium speed.	Lighter	2 minutes
Week 48	1 Warm Up Set: 8 – 12 reps. 1 Heavy Set: 8 – 12 reps. Slower Speed.	Moderate/Heavy	2 minutes
Week 49	3 Sets on each exercise of 6, 8, 12 repetitions. Lower weights each set. Medium speed.	Moderate	3 minutes
Week 50	1 set 90 seconds focused on resistance. Medium speed.	Lighter	2 minutes
Week 51	1 Warm Up Set 8 reps 1 Heavy Set 8 reps	Heavy	3 minutes
Week 52	Cardio Exercises. 10 exercises in a set. 2 Sets.	Moderate	3 minutes

GH Method: List of Strength/Resistance Exercises

MEN

WOMEN

Exercise

Exercise

Chest: Smith Bench Press/Incline	Glutes: Abductor
Glutes: Abductor	Biceps: Cable Easy Curl / Free Bar
Biceps: Cable Easy Curl/Free Bar	Quads: Leg Extension
Quads: Leg Extension	Chest: Smith Press
Calves: Calf Machine	Abs: Decline
Biceps: Preacher	Quads: Leg Press
Quads: Leg Press	Back: Pull Down Behind
Quads: Leg Extension	Hamstring: Machine
Abs: Decline	Shoulders: Dumbbell Press / Smith Press
Back: Pull Down Behind	Triceps: Push Down / Kick Back / Rope Pull down
Hamstring: Curl Machine	Back: Low Roll
Shoulders: Dumbbell Press / Smith Press	Abs: Sit-Ups
Back: Low Roll	Shoulders: Side Raise with Dumbbells
Hamstring: Good Morning with Dumbbell/ 1 Leg Hamstring Curl	Triceps: Close Grip
Shoulders: Side Rise with Dumbbells	Hamstring: Good Morning with Dumbbells/1 Leg Hamstring
Triceps: Push Down / Kick Back	Triceps: Push Down / Kick Back
Abs: Sit Ups	Abs: Sit Ups
Triceps: Close Grip	Triceps: Close Grip

5)Statistical analyses:

The efficacy of the methods will be determined by:

1. a significant difference in term of pre and post treatment perception of well being between the groups
- 2.a significant difference in the lean/fat body mass ratio between the groups
3. a significant difference in BMI between the groups
4. a significant difference between the inflammatory parameters between the groups
5. a significant difference between the metabolic parameters between the groups

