
The data will be entered into an Excel spreadsheet and stored on the UIMCC hospital server. The patient data, including age, sex, race, underlying kidney disease, length of hospital stay, rejection episode, comorbidities, and medications will be coded and patient names will not be included in the datasheet.

The de-identified collected data will be entered into a SAS database. Initial descriptive analysis will include calculating means, standard deviations, ranges and frequencies. T-tests for continuous variables and Chi Square or Fischer exact tests of association for

categorical variables will be used to compare results of the study between the two groups for the efficacy parameters listed above. A P value<0.05 will be considered significant.

6) Benefits/risks

The main risk of this research is loss of confidentiality of medical information. Consent will be obtained for all patients. Master patient code list will be kept in a separate file accessible only by the primary investigator. A member of the transplant team will be available to answer any questions or discuss any concerns that patients may have.

The patient may experience mild anxiety or discomfort in providing information about their health and well-being. The patient may also have a potential to feel anxiety when being video recorded (if applicable).

Risks associated with the exercise program

The likely risks and discomforts expected in this study are those that largely involve being engaged in an exercise program after a prolonged period of inactivity. Such risks include: strains, sprains, and muscle soreness. Serious physical injury is considered unlikely given the screening for inclusion and physician approval. We will attempt to reduce risks of injury and harm by promoting gradual increases in exercise across time throughout the 3 month period and having exercise be instructed and supervised by trained professional fitness personnel.

Risks associated with the blood draw:

The risks associated with a blood draw include: mild pain, bleeding or bruising at the site of the draw. In general, any bruising should completely disappear within several days. There are minimal risks of fainting or hypotension (low blood pressure) during or after the blood draw.

Risks associated with the Maximal Aerobic Capacity Test (VO2 Test) and the 6 minute walk test include:

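### Section 5 names only two-group t-tests and, for efficacy criteria 2-5, fixes no visit, scale or role for baseline; a pre-specified 12-month ANCOVA would settle this at little cost

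*Combined protocol and SAP*

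**What the plan says.** Section 5) Statistical analyses lists five efficacy criteria and then the tests: "T-tests for continuous variables and Chi Square or Fischer exact tests of association", with significance at P<0.05. No regression, ANCOVA or repeated-measures model appears anywhere in the document.

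- Criterion 1 alone refers to two time points: "a significant difference in term of pre and post treatment perception of well being between the groups".
- Criterion 2 reads "a significant difference in the lean/fat body mass ratio between the groups". Criteria 3 (BMI), 4 (inflammatory) and 5 (metabolic) follow the same pattern, with no visit, no scale and no covariate.

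The rest of the protocol gives hints on timing:

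- Hypothesis 2 says "we will test whether muscle strength (Biodex measurements) and muscle mass (DEXA scan) changes after 12 months of an exercise intervention" and places the last measurement at 12 months. Hypothesis 5 predicts lower HbA1c and fasting glucose than in the comparison groups.
- Parameters to analyze in all patients (for PROMIS) and Body composition and strength (for BMI) treat month 12 as the end of the study.
- BMI, DEXA, PROMIS and the inflammatory markers are scheduled at a pre-treatment visit, 6 months and 12 months. The metabolic labs have no study dates and follow routine transplant care (Metabolism and renal function changes).
- Under Long-term follow-up, every 6 months for two more years, "medical records will also be reviewed to confirm BMI and graft function". Controls are offered the GH programme after their last control visit (Randomization, control group).

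**The concern.** For criteria 2-5 a reader of section 5 cannot tell which of several t-tests is the planned one. At least four are available for each of criteria 2-4: final value or change, at 6 or 12 months. If that choice is left until the data are in, the nominal 5% no longer holds for the endpoint.

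The second issue is efficiency. Allocation is 4:1, so precision is governed largely by the 45 controls. A baseline value is already scheduled for most endpoints, but section 5 gives it no role. A final-value t-test discards it, and a change t-test uses it with a fixed weight of one, whatever the correlation.

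**Working it through.** **Inputs from the document.** 225 patients, 180 GH and 45 control (METHODS, Setting); 4:1 allocation (Randomization); P<0.05 (section 5). The split is consistent: 225 × 4/5 = 180 and 225/5 = 45. The document gives no power, effect size or SD, so there is no sample-size calculation to reproduce.

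**Assumptions.** Two-sided test (sidedness is not stated), complete data, normal outcomes with equal SD at each visit, and baseline-to-follow-up correlation ρ of 0.3 to 0.9. The document gives no correlation.

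**1. What is fixed and what is open**

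| Criterion | Visit in section 5 | Scale in section 5 | Values available |
|---|---|---|---|
| 1 Well-being | pre and post | suggests change | pre-treatment, 6, 12 months |
| 2 Lean/fat ratio | none | none | pre-treatment, 6, 12 months |
| 3 BMI | none | none | pre-treatment, 6, 12 months, then 6-monthly from records |
| 4 Inflammatory | none | none | pre-treatment, 6, 12 months |
| 5 Metabolic | none | none | undated routine labs |

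**2. Type I error if the test is picked after the results.** Simulation with no true effect, 180 v 45, equal correlations, 20,000 trials per setting:

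| ρ | Better of final value and change, 12 months | Same, 6 or 12 months | Single 12-month ANCOVA |
|---|---|---|---|
| 0.3 | 9.1% | 16.3% | 5.2% |
| 0.5 | 9.2% | 16.4% | 5.0% |
| 0.7 | 9.7% | 16.1% | 5.2% |
| 0.9 | 9.6% | 15.2% | 5.0% |

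With 100,000 trials, and correlations either equal or decaying over time, the first two columns range over 8.7-9.7% and 14.0-16.2%. As a plausibility check, two independent tests would give 1 − 0.95² = 9.75%. Final value and change correlate at only √((1−ρ)/2), which is 0.59 at ρ = 0.3 and 0.22 at ρ = 0.9, so values just below 9.75% are expected.

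**3. Precision with a common baseline slope.** Standard error factor √(1/180 + 1/45) = 0.1667. Difference detectable with 80% power = (1.960 + 0.842) × 0.1667 × √V = 0.467 × √V, in SD of the outcome. V is 1 for the final value, 2(1−ρ) for change and 1−ρ² for ANCOVA (large sample).

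| ρ | V change | V ANCOVA | Final | Change | ANCOVA |
|---|---|---|---|---|---|
| 0.3 | 1.40 | 0.91 | 0.467 | 0.552 | 0.445 |
| 0.5 | 1.00 | 0.75 | 0.467 | 0.467 | 0.404 |
| 0.7 | 0.60 | 0.51 | 0.467 | 0.362 | 0.333 |
| 0.9 | 0.20 | 0.19 | 0.467 | 0.209 | 0.204 |

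The variance of a change t-test exceeds that of ANCOVA by the factor 2/(1+ρ): 1.54, 1.33, 1.18 and 1.05.

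**4. Precision if slopes differ between arms.** Let b1 be the GH slope, b0 the control slope, and b = 0.8·b1 + 0.2·b0. ANCOVA without an interaction has variance (1 − 2b·b1 + b²)/180 + (1 − 2b·b0 + b²)/45. For b1 = 0.2 and b0 = 0.9, b = 0.34, which gives 0.9796/180 + 0.5036/45 = 0.01663. Divided by 0.1667², this is 0.599. The change t-test gives (1.6/180 + 0.2/45)/0.1667² = 0.480, and ANCOVA with a centred baseline-by-arm term 0.422. With b1 = 0.6 and b0 = 0.9 the three values are close: 0.327, 0.320 and 0.294. So at 4:1 plain ANCOVA can lose to a t-test, but materially only when slopes differ strongly.

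**The case against.** **The protocol is not silent on timing.** Hypothesis 2 concerns body composition by DEXA, the same scan that supplies criterion 2, and sets the final measurement at 12 months. Hypothesis 5 gives a direction for two metabolic labs, and month 12 is called the study end for BMI itself. This stands: 12 months is the natural reading. But section 5 does not refer to any of it, and a reader who accepts 12 months still has to choose between final value and change. That choice alone carries the 9-10%.

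**A pre-stated t-test would do.** True for validity. The remaining argument for ANCOVA is precision, which rests on an unknown correlation and nearly vanishes against a change score at 0.9.

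**Stronger readings that a reader might infer, and that the documents do not support:**

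- *That BMI error could reach 23-31%.* Simulation gives that range if any 6-monthly BMI up to 36 months could be selected. But the later values sit under Long-term follow-up, section 5 does not name them as efficacy data, and they come when controls may have taken up GH.
- *That enrolment and baseline are different visits.* The text says of PROMIS "PROMIS 29 Profile v2.0 will be administered to all patients at the time of enrollment", while of BMI and other measures it says "These measures will be completed at baseline, 6 months and 12 months post-intervention", and enrolment may precede transplant. However, the schedule table puts consent, BMI and questionnaires in one Baseline column. A confirming sentence is enough.
- *That a baseline-by-arm term should be the default.* No text suggests unequal slopes. On simulated skewed data the interaction model gave 5.2-6.2% type I error, against 4.7-5.1% for plain ANCOVA.
- *That tests have been selected after the fact.* Nothing in the document says so; the error rates are conditional.

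**Conclusion.** The point holds for section 5 as written. Criteria 2-5 have no stated visit, scale or baseline role, and the nearest text implies a 12-month comparison without fixing the test. The t-tests are not invalid; what is at risk is the nominal error rate if the choice is left open, and some avoidable loss of precision.

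The size is about 9-10% or 14-16% type I error per endpoint under after-the-fact choice. The detectable difference (final / change / ANCOVA) is 0.47/0.55/0.45, 0.47/0.47/0.40, 0.47/0.36/0.33 and 0.47/0.21/0.20 SD at correlations of 0.3, 0.5, 0.7 and 0.9. These figures assume those correlations, complete data and 180 v 45; the precision figures also assume a common baseline slope. This is a worthwhile improvement, not a flaw that invalidates the trial.

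It does not settle which inflammatory or metabolic markers count, or multiplicity across them; criteria 4 and 5 name none.

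**What to change.** Add a paragraph to section 5:

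- For each continuous endpoint with a scheduled baseline, replace the t-test with the 12-month between-arm contrast from ANCOVA adjusted for that endpoint's own baseline, with robust standard errors. Analyse skewed markers on the log scale.
- Treat 6-month and long-term follow-up values as descriptive, because controls may take up GH after their last control visit.
- For the routine metabolic labs, define which values count as baseline and as 12 months, then use the same model.
- Confirm that the enrolment and baseline values of BMI and PROMIS are the same measurement or, if not, say which is the covariate.
- Offer a centred baseline-by-arm interaction as an optional sensitivity analysis, because plain ANCOVA can lose precision at 4:1 if slopes differ strongly.
- Long-term follow-up refers to patients who had completed the study by July 2014. Fix the model before outcomes are compared by arm, and state whether any such comparison has already been seen. If it has, the change is not clean pre-specification.

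Cost: a short SAP paragraph, a lab-value definition and a little SAS code. No new visits, data or patients.

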4. Patients with strength training will activate type II macrophages which are anti-inflammatory and pro-regenerative, tipping the balance away from inflammation towards regeneration when compared to the other treatment groups. Since strength training is likely to initiate signals of muscle regeneration, and since type II macrophages play a key role in this effect, it is possible that increasing the signaling to the muscle for regeneration may also increase the proportion of active type II macrophages which are anti-inflammatory. To test this hypothesis, we will test the proportion of peripheral blood M1/M2 macrophages at baseline, 6 months and 12 months after the initiation of the intervention. Recognizing that immunosuppression may significantly confound this proportion and overall suppress it, we will also test circulating levels of pro-inflammatory cytokines such as C-reactive protein(CRP), IL-6, IL-1, TNF-alpha, homocysteine, adiponectin, leptin, and resistin as well as pro-regenerative cytokines such as TGF-beta and IL-10.

5. We expect patients with strength training will experience less renal dysfunction, decreased hemoglobin A1C, increased peripheral vascular function, decreased fasting blood sugar when compared to the other treatment groups. The rationale for this hypothesis is the finding that muscle mass provides active regulation of glucose and other metabolites. Therefore increasing this may provide improved metabolic function. These laboratory panels are part of the standard transplant follow-up labs and add no cost to the project.

6. Patients with strength training will have an overall improved sense of well-being and energy level compared to those with physical therapy or no treatment. With twice weekly counseling for activity and nutrition, patients will be asked about their general health, mental health and pain intensity using the PROMIS questionnaires.

METHODS

Setting: The study will include 225 patients, to achieve a goal of 180 patients in the GH study group and 45 patients in the control group. Every patient will be followed for 3 years after the start of the intervention. Patients will start the intervention at least 2 months post-transplant; however they can be enrolled prior to transplant.

Main Study Inclusion criteria:

- Successful kidney transplantation (KTx) with primary graft function
- Age between 18 and 65 years

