- Adequate cognitive ability to complete the questionnaires, give consent for the study and follow the physical and diet instructions

Main Study Exclusion criteria:

- transplant of any other organ besides kidney alone or a combination of a kidney/pancreas

- non-ambulatory or significant orthopedic problems
- cardiac/pulmonary disease that contraindicate the physical training
- any contraindication to exercise testing per the American Heart Association
- unable to comply with the training program

Muscle Biopsy Inclusion:

- Age between 18 and 65 years
- Patients who have a brachial–cephalic arteriovenous fistula (AVF) in the elbow or brachial–basilic AVF in the arm
- Exercise Arm- the biopsy will only be performed once, after the 12 month exercise intervention is completed (which will be longer than 1 year post transplant surgery)
- Control Arm- this procedure will be performed once, around one year post transplant surgery (may occur at any time during the study)

Muscle Biopsy Exclusion:

- Patients that do not meet the inclusion criteria

Identifying potential subjects for recruitment:

A waiver for an alteration of consent and waiver of documentation of consent is being requested for review of medical records to identify potential patients for study recruitment and also for a telephone screening process for patients that response to a recruitment flyer. The principal investigator already has access to these records as part of daily care for all patients seen in clinic. This presents no more than minimal risk since this data will be kept confidential.

Moreover, as part of the telephone screening process for patients interested in this study there will be oral consent obtained to start the screening process in order to determine if the patients are eligible to be in the study. If the patients are eligible, they will be schedule for a visit where they will be consented to be in the study.

Randomization: All patients who meet the enrollment criteria will be randomized 4:1 to the GH group or the control group.

- GH group: patients will be treated for 12 months with the GH method (Appendix 1) for one hour twice a week

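### Section 5 plans plain two-group t-tests and names no analysis visit, as-randomised set or missing-data method, so unequal drop-out from a 104-session programme could bias the comparison

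*Combined protocol and SAP*

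**What the plan says.** The inferential plan in section 5 (Statistical analyses) is very short. It lists "T-tests for continuous variables and Chi Square or Fischer exact tests of association for" categorical variables, says that these "will be used to compare results of the study between the two groups for the efficacy parameters listed above", and adds that "A P value<0.05 will be considered significant". The five efficacy criteria are well-being, lean/fat ratio, BMI, inflammatory parameters and metabolic parameters. Only the well-being criterion mentions time, as a pre/post comparison. No visit, analysis set, missing-data method or repeated-measures model is named, and no drop-out rate is given.

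The Methods schedule repeated measurement in both arms. The PROMIS questionnaires, BMI and the inflammatory markers are taken at baseline, 6 and 12 months. For the body-composition and fitness tests, including DEXA, "These 7 tests will be done at baseline, 6, and 12 months". The metabolic laboratory values follow standard of care, with no fixed 6-month visit.

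On size and burden, "The study will include 225 patients, to achieve a goal of 180 patients in the GH study group and 45 patients in the control group", randomised 4:1. In the GH arm "patients will be treated for 12 months with the GH method (Appendix 1) for one hour twice a week". The control arm receives standard care and is offered GH after its final control visit.

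**The concern.** The two arms make very different demands. GH patients attend in person twice a week for a year. Controls attend only the assessments and have a reason to stay, because GH is offered to them afterwards. The Background itself says that this population is hard to bring into regular exercise programmes. Loss that differs by arm and depends on how the patient is doing is therefore a realistic possibility.

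If that happens, a t-test on the available 12-month values compares the GH patients who did well enough to stay with most of the controls. Part of any apparent benefit would then be selection. The scheduled 6-month value says how a patient was doing before leaving, but a two-sample t-test has no place for it. Because visit, analysis set and missing-data method are all unstated, they could also be chosen after the data are seen.

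**Working it through.** **Inputs from the documents.** 180 GH and 45 control patients; significance at 0.05 (taken as two-sided, since sidedness is not stated). Sessions: 4 in the first 2 weeks, then 2 × 50 = 100, total 104, which agrees with 2 × 52 = 104.

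**Inputs assumed, because the documents give none.** Outcome SD 1 at each visit; correlations 0.70 (baseline to 6 months), 0.75 (6 to 12) and 0.60 (baseline to 12); 10% random loss in controls; 15, 25 or 35% loss in GH, with odds of leaving 2.7 times higher per SD worse 6-month course given baseline; true effect zero.

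**Scale.** With all 225 patients and 80% power, the detectable difference is (1.960 + 0.842) × √(1/45 + 1/180) = 2.802 × 0.1667 = 0.47 SD of the variable analysed.

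**Bias of the t-test on change.** Let r = (y6 − 0.70·y0)/√(1 − 0.70²). It is uncorrelated with baseline, and its covariance with the 12-month value is (0.75 − 0.70 × 0.60)/√0.51 = 0.33/0.714 = 0.462. The bias is 0.462 × the mean of r among GH patients who stay (by numerical integration). The SD of change is √(2 − 2 × 0.60) = 0.894, so SE = 0.894 × √(1/n_GH + 1/40.5). The false-positive rate is Φ(bias/SE − 1.96) + Φ(−bias/SE − 1.96).

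| GH loss | GH patients left | mean r | bias (SD) | SE | bias/SE | false-positive rate |
|---|---|---|---|---|---|---|
| 15% | 153 | 0.133 | 0.061 | 0.158 | 0.39 | 6.7% |
| 25% | 135 | 0.213 | 0.099 | 0.160 | 0.61 | 9.4% |
| 35% | 117 | 0.292 | 0.135 | 0.163 | 0.83 | 13.2% |

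Repeated simulation runs gave 0.06 / 0.10 / 0.13 to 0.14 SD and 6.5 to 7.5 / 9.2 to 10.4 / 13.0 to 13.8%. With the odds ratio cut to 1.6, the error is 5.6 to 8.0%.

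**Adjusting for baseline alone.** ANCOVA in patients with a 12-month value gave 6.9 / 11.2 / 15.6%. Because r is unrelated to baseline, the bias stays while the standard error falls.

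**Using the 6-month value by likelihood.** Bias was at most 0.003 SD and error 4.6 to 5.1%, when every drop-out has a 6-month value and leaves because of it.

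**Varying the drop-out assumption (t-test on change).**
- Random loss, 25% GH and 10% control: 0.00 SD, error 4.2%.
- Same response-driven mechanism, 25% in both arms: 0.00 SD, error 5.1%.
- Same mechanism, 25% GH and 10% control: 0.099 − 0.462 × 0.091 = 0.057 SD, error about 6.6%.
- Same mechanism, 15% GH and 25% control: 0.061 − 0.099 = −0.04 SD, against GH.
- Harsher case in a simpler two-visit model (6- and 12-month changes, SD 1, correlation 0.6), where the worst 6-month responders leave GH and nobody leaves control: 0.12 / 0.21 / 0.30 SD at 10 / 20 / 30% loss, error about 12 / 27 / 46%.

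**Limits of the likelihood model.** At 25% GH loss (t-test bias 0.10 SD), it keeps about 0.04 SD of bias if half the drop-outs leave before the 6-month test and 0.10 SD if all do. In the two-visit model, if 20% leave GH only, because of the unseen 12-month value, the t-test is off by 0.36 SD and the likelihood model still by 0.27 SD.

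**The case against.** The strongest reply is that the plan is silent rather than wrong. Several stronger readings are tempting and are not supported.

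- *That the plan restricts the analysis to completers and discards the 6-month data.* No such rule is written. Separate 6-month tests or imputation are not ruled out. Dropping patients is what a t-test does when nothing else is specified.
- *That 6-month values exist for everyone.* They are scheduled for four of the five criteria. Metabolic values come from routine care, and a patient lost before month 6 has no 6-month value.
- *That GH patients who stop training leave the assessments.* No passage ties the tests to session attendance. The Setting paragraph has every patient followed for 3 years, and routine metabolic values need not be lost. However, the follow-up after month 12 is by phone and record review, which cannot replace missing DEXA, cytokine or PROMIS values. No sentence says that patients who stop sessions are still invited at 6 and 12 months.
- *That the result will shift towards GH.* The documents give no drop-out rate or mechanism. The shift needs more response-driven loss in GH than in control.
- *That a repeated-measures model cures the problem.* It does so only for loss explained by observed values, and multiple imputation with the same information would serve as well.

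These points narrow the claim. They leave standing that the one named method for continuous outcomes cannot combine the visits, and that visit, analysis set and handling of missing values are unspecified.

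**Conclusion.** The gap in section 5 is certain; the bias is conditional. Under the stated assumptions the t-test on change favours GH by about 0.06 to 0.14 SD, with a false-positive rate of about 7 to 14% instead of 5%. At the top of that range the shift is nearly a third of the 0.47 SD detectable difference (0.14/0.47 = 0.30). Milder dependence on response brings the error to 5.6 to 8.0%; random or equal loss removes the shift; heavier response-driven loss in controls reverses it. All drop-out rates, correlations and mechanisms are assumptions. The change is worth making because it uses data already scheduled, and because patients lost from assessment cannot be recovered at the analysis stage. Confidence is medium.

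**What to change.** In section 5, write:

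> All randomised patients are analysed in the arm assigned. Continuous criteria measured at baseline, 6 and 12 months use a repeated-measures likelihood model (arm, visit, arm × visit, baseline value × visit; unstructured covariance), or multiple imputation that includes the 6-month value; the 12-month arm contrast is the test. Metabolic criteria use the 12-month value adjusted for baseline. A sensitivity analysis (for example delta-adjusted imputation in GH drop-outs) examines drop-out that depends on unobserved values.

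Because metabolic values are routine, also say which one counts as the 12-month value. State that the main model removes bias only for drop-out explained by observed values, and that patients lost before month 6 contribute little.

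In Methods, write:

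> Patients who stop GH sessions are still invited to the 6- and 12-month assessments.

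The cost is a few sentences, slightly more analysis work and some effort to bring back patients who stopped training. No new tests are needed.
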